4.1 Inclusion Criteria

101. Subject has provided informed consent prior to initiation of any study-specific activities/procedures.
102. Subjects \geq 18 years of age at the time of signing consent.
103. AML as defined by the WHO Classification ([Appendix D](#)) persisting or recurring following 1 or more treatment courses except promyelocytic leukemia (APML).
 1. More than 5% myeloblasts in bone marrow.
104. Eastern Cooperative Oncology Group (ECOG, [Appendix F](#)) Performance Status of \leq 2.
105. Renal function as follows: serum creatinine $<$ 2.0 mg/dL (176.84 μ mol/L) and estimated glomerular filtration rate $>$ 30 mL/min/1.73 m².
106. Hepatic function as follows:
 - Aspartate aminotransferase (AST) and Alanine aminotransferase (ALT) \leq 3.0 x upper limit of normal (ULN)
 - Bilirubin \leq 1.5 x ULN (unless considered due to Gilbert's syndrome or hemolysis)

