4.2 Exclusion Criteria

201. Active extramedullary AML in the central nervous system (CNS).
202. Known hypersensitivity to immunoglobulins.
203. White blood cells (WBC) $>$ 15,000 cells/mcL (15 cells \times 10⁹/L) at screening. In subjects with WBC $>$ 15,000 cells/mcL at screening with lymphocyte predominance, subject may be deemed eligible for the trial by the Amgen physician, after discussion with the investigator.
204. Prior malignancy (other than in situ cancer) unless treated with curative intent and without evidence of disease for $>$ 2 years before screening.
205. Autologous HSCT within 6 weeks prior to start of AMG 673 treatment.
206. Allogeneic HSCT within 3 months prior to start of AMG 673 treatment.
207. Non-mangeable graft versus host disease.
208. History or evidence of cardiovascular risk including any of the following:
 - History or evidence of clinically significant arrhythmias (ventricular fibrillation, ventricular tachycardia, supraventricular tachycardia, atrial tachycardia/flutter, atrial fibrillation with rapid ventricular response, second or third degree atrioventricular block, and sick sinus syndrome).
 - Exception: Subjects with controlled atrial fibrillation for $>$ 30 days prior to study day 1 are eligible. Controlled atrial fibrillation is defined as atrial fibrillation with no rapid ventricular response which requires no change in medication/dosage or addition of new medication or hospital admission within 30 days prior to study day 1.

- History of acute coronary syndromes (eg, myocardial infarction and unstable angina) and/or coronary angioplasty within 6 months prior to study day 1.
 - History or evidence of \geq Class II congestive heart failure as defined by New York Heart Association (NYHA).
 - Chronic hypertension (defined as a systolic blood pressure [SBP] >140 mm Hg and/or diastolic blood pressure [DBP] >90 mm Hg which cannot be controlled by anti-hypertensive therapy).
 - Subjects with intra-cardiac defibrillators.
 - Abnormal cardiac valve morphology (\geq grade 2) (subjects with grade 1 abnormalities [ie, mild regurgitation/stenosis] can be entered on study. Subjects with moderate valvular thickening should not be entered on study).
209. History of arterial thrombosis (eg, stroke or transient ischemic attack) in the past 3 months.
210. Active infection requiring intravenous antibiotics within 1 week of study enrollment (day 1).
211. Known positive test for human immunodeficiency virus (HIV).

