- The Amgen medical monitor must be consulted prior to re-starting treatment
- If CRS occurred during AMG 673 infusion, infusion has been interrupted for at least 72 hours
- The event has resolved to grade ≤ 1 prior to re-starting treatment

AMG 673 therapy should be restarted 1 dose level below the dose at which the event occurred. If this lower dose level is well tolerated (ie, absence of grade ≥ 3 CRS), then a dose step up to the subject's target dose level can occur. An intermediate dose may be administered after consultation with the Amgen medical monitor prior to stepping up to the target dose.

Please also refer to the general guidance for re-start of treatment after adverse events in [Section 6.2.1.4](#)

For Grade 3 and 4 CRS, please see [Section 2](#) for DLT considerations.

Tumor Lysis Syndrome

Subjects with AML and WBC $<10,000/\text{mcl}$ or $10 \text{ cells} \times 10^9/\text{L}$ are considered to be at low risk for tumor lysis syndrome. WBC $>10,000/\text{mcl}$ and $<50,000/\text{mcl}$ are considered to be at intermediate risk, and subjects with WBC $>50,000/\text{mcl}$ are considered at high risk. This protocol requires that subjects have a maximum WBC count of $15,000/\text{mcl}$ or $15 \text{ cells} \times 10^9/\text{L}$.

Additional high-risk features include baseline uric acid $>450 \text{ mcg/L}$ (7.5 mg/dl), serum creatinine $> 1.4 \text{ mg/dL}$, and lactate dehydrogenase (LDH) greater than the ULN.

Patients with intermediate risk WBC count and elevated baseline uric acid ($> 450 \text{ mcg/L}$), serum creatinine $>1.4 \text{ mg/dl}$, or LDH greater than ULN will be recommended to receive allopurinol prophylaxis. Typical dosing is 600-800 mg/day administered BID or QID and should begin 3 days before the first dose of study drug. Patients should be well hydrated and supplemented with intravenous fluid as clinically indicated.

For grade 3 and 4 tumor lysis syndrome, please see [Section 6.2.1.3](#) for DLT considerations.

Infection Prophylaxis

Subjects who may experience neutropenia for 7 days or longer are at a high risk for infectious complications. As appropriate, these subjects should be administered prophylactic antibacterial (eg, fluoroquinolones), antifungal and antiviral medications. These subjects should be monitored for early signs of breakthrough infections after the initiation of antibacterial therapy to prompt additional evaluation and possible therapy modification.

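### The uric acid cut-off for allopurinol prophylaxis is printed in the wrong unit: 450 mcg/L is not 7.5 mg/dL, and 450 micromol/L is evidently meant

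*Protocol*

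**What the plan says.** The relevant text is the Tumor Lysis Syndrome part of Protocol Section 6.6. It grades risk by white cell count (WBC): low below 10,000/mcl, intermediate from 10,000 to 50,000/mcl, high above that. It then adds three further risk markers. The first is uric acid ("Additional high-risk features include baseline uric acid"), with a cut-off of more than 450 mcg/L and 7.5 mg/dL in brackets. The other two are serum creatinine above 1.4 mg/dL and LDH above the upper limit of normal.

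The next paragraph is the rule that sites act on. It starts "Patients with intermediate risk WBC count and elevated baseline uric acid", gives the cut-off as more than 450 mcg/L with no mg/dL equivalent, and lists the creatinine and LDH criteria as alternatives. Subjects meeting any one of the three are recommended allopurinol: "Typical dosing is 600-800 mg/day administered BID or QID and should begin 3 days before the first dose of study drug".

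Two other provisions limit who is affected. Section 6.6 restates the entry cap ("This protocol requires that subjects have a maximum WBC count of" 15,000/mcl). Exclusion criterion 203 in Section 4.2 allows an exception above that cap, where a subject "with lymphocyte predominance, subject may be deemed eligible for the trial by the Amgen physician" after discussion with the investigator.

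No other section gives a uric acid threshold or corrects this one.

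**The concern.** A threshold printed with two values that cannot both be true leaves the site to choose between them. Here the conflict is repeated in the instruction that triggers treatment, and that sentence carries only the suspect unit. An investigator who goes straight to the allopurinol rule sees a cut-off far too low to separate normal from raised uric acid.

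Uric acid is a local-laboratory test (Table 15), and Section 3.2 places sites in Australia, Germany, Japan and the US. The documents do not say which units those laboratories report. If they differ, sites will have to convert the threshold themselves, and the printed unit then matters.

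What is at stake is over-use of allopurinol in a first-in-human study in which tumor lysis syndrome is a listed potential risk (Table 1). Nothing inferential depends on it.

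**Working it through.** **Inputs from the documents**
- Uric acid cut-off: 450 mcg/L, equated to 7.5 mg/dL (Section 6.6, risk markers).
- The same cut-off, 450 mcg/L only (Section 6.6, allopurinol rule).
- Creatinine limit: 2.0 mg/dL, equated to 176.84 micromol/L (Section 4.1, criterion 105, "Renal function as follows: serum creatinine").

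**Inputs assumed, not in the documents**
- Molar mass of uric acid: 168.11 g/mol.
- Illustrative baseline uric acid range: 2 to 7 mg/dL, all below the intended cut-off.

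**Step 1. Try to reproduce the printed pair.** To go from mg/dL to mcg/L, multiply by 10 (dL to L) and by 1,000 (mg to mcg).
- 7.5 mg/dL = 7.5 × 10 × 1,000 = 75,000 mcg/L, not 450.
- 450 mcg/L = 450 / 10,000 = 0.045 mg/dL, not 7.5.
- Ratio: 75,000 / 450 = 166.7.

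The pair does not reproduce. This step is metric arithmetic and needs no outside constant.

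**Step 2. Find the unit that fits 450.** Express 7.5 mg/dL in the plausible units:

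| Unit | Value of 7.5 mg/dL |
|---|---|
| mcg/L | 75,000 |
| mcg/dL | 7,500 |
| mcg/mL | 75 |
| mg/L | 75 |
| micromol/L (75,000 / 168.11) | 446.1 |

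Only micromol/L comes near 450; 446.1 / 450 = 0.991, so the gap is under 1%. In the other direction, 450 micromol/L = 450 × 168.11 / 10,000 = 7.56 mg/dL. Put another way, if 450 is in micromol/L, the printed pair implies a molar mass of 75,000 / 450 = 166.7 g/mol, against the assumed 168.11.

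**Step 3. Check the protocol's own convention.** Criterion 105 pairs mg/dL with micromol/L: 176.84 / 2.0 = 88.42 micromol/L per mg/dL. As mcg/L, 2.0 mg/dL would be 20,000. So the protocol elsewhere gives a blood chemistry limit in mg/dL with its molar equivalent, which is the pairing that fits uric acid.

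**Step 4. What the literal cut-off would do.** Compare the assumed range with 450 mcg/L:
- 2 mg/dL = 20,000 mcg/L; 20,000 / 450 = 44.
- 7 mg/dL = 70,000 mcg/L; 70,000 / 450 = 156.

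Values that should not trigger the criterion exceed the literal cut-off 44- to 156-fold, so on that reading the criterion is always met.

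**Step 5. Who is affected.** The rule applies only to the intermediate WBC group. With the entry cap, that is about 10,000 to 15,000/mcl, plus any subject admitted under the criterion 203 exception. Within that group, subjects with creatinine above 1.4 mg/dL or raised LDH qualify anyway. The literal unit changes the recommendation only for the remainder, and the documents give no figures from which to count them.

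**The case against.** The best defence is that the text nearly corrects itself. The intended 7.5 mg/dL is printed at first mention; the allopurinol rule follows in the next paragraph, repeats the number 450 and describes the uric acid as elevated. An investigator would have to overlook all of this to apply 0.045 mg/dL, and many would recognise the intended value on sight. The rule is also a recommendation, the group it reaches is small, and the error leans towards more prophylaxis. The 167-fold and 44- to 156-fold figures measure the size of the slip, not the number of subjects managed differently. Finally, micromol/L as the intended unit rests on a molar mass that the documents do not supply.

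Most of this stands, and it keeps the point minor. It does not make the printed threshold right. The sentence that triggers action carries only the wrong unit, and the mismatch between mcg/L and mg/dL is established without any outside constant. A text-extraction fault is unlikely, because the unit appears twice in separate sentences while micromol/L came through intact in criterion 105. The claim that essentially every intermediate-risk subject would qualify is conditional: it holds only on a literal reading that sets aside the nearby bracket.

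**Conclusion.** The concern holds: the unit is wrong as written, in both places. The two printed values differ by a factor of 167; with micromol/L they agree within 1%. That the pair is inconsistent is certain. That micromol/L was intended is an inference from the assumed molar mass, supported by the creatinine pairing in criterion 105 and by the failure of every other unit tried.

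The consequence is possible over-recommendation of allopurinol to those intermediate-WBC subjects who do not already qualify by creatinine or LDH, at sites that apply the unit literally. How many that would be cannot be estimated from the documents. The WBC risk groups are also unaffected. Severity: minor.

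**What to change.** In Section 6.6, replace mcg/L with micromol/L in both sentences and repeat the bracket in the allopurinol rule, so that each reads `>450 micromol/L (7.5 mg/dL)`. If the sponsor prefers not to rely on a molar conversion, stating the cut-off as more than 7.5 mg/dL in both sentences would also remove the conflict.

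The cost is a unit correction in two places and one added bracket, which can go into the next amendment. No procedure, data collection or analysis changes.

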6.7 Medical Devices

Depending on the dose, the investigational product must be administered using either syringe pumps (for lower doses) or infusion pumps (for higher doses) approved for use by the appropriate regulatory authorities for the country in which the subject is undergoing treatment. Investigational product infusion for solution will be prepared in syringes or bags for IV infusion and delivered through infusion lines.

Additional details for the use of the above mentioned medical devices and specific set of device specifications are provided in the IPIM.

Additional medical devices (eg, syringes, sterile needles, alcohol prep pads), that are commercially available are not provided or reimbursed by Amgen (except, if required by local regulation). The investigator overseeing the conduct of the study at each respective institution will be responsible for obtaining these supplies.

6.8 Product Complaints

A product complaint is any written, electronic or oral communication that alleges deficiencies related to the identity, quality, durability, reliability, safety, effectiveness, or performance of a drug(s) or device(s) after it is released for distribution to market or clinic by either Amgen or by distributors and partners for whom Amgen manufactures the material.

This includes any drug(s), device(s), or combination product(s) provisioned and/or repackaged /modified by Amgen. Drug(s) or device(s) includes investigational product.

Any product complaint(s) associated with an investigational product(s) or non-investigational product(s) or device(s) supplied by Amgen are to be reported according to the instructions provided in the IPIM.

Approved

6.9 Excluded Treatments, Medical Device Use, and/or Procedures During Study Period

Any anti-tumor therapy other than the investigational product, including cytotoxic and/or cytostatic drugs, hormonal therapy, immunotherapy or any biological response modifiers, any other investigational agent, chronic systemic corticosteroid therapy, other immunosuppressive therapies, or stem-cell transplantation is not allowed.

Exception: Hydroxyurea is allowed to control WBCs as described in [section 6.3](#).

Radiotherapy is not permitted except for palliation of symptoms and should be discussed with the Amgen medical monitor first. Investigators should ensure that the need for radiation does not indicate progressive disease and that for subjects with measurable disease, radiation is not to the sole site of measurable disease.

The following procedures should also not be undertaken within the timeframes specified prior to enrollment and during the study:

- Participation in an investigational study (drug or device) within 14 days of study day 1
- Major surgery within 28 days of study day 1 (with the exception of biopsy or insertion of central venous catheter)
- Treatment with another investigational drug or device during the study

7. STUDY PROCEDURES

7.1 Schedule of Assessments

Approved

Table 6. Schedule of Assessments: Doses D1-D5 (Cycle 1)

Cycle Day	SCR	Treatment Period																												EoT	EoS			
	-14 to -1	1							2	3	4	5 ^a								6	7	8	14 ^b											
	Pre-dose	Relative to start of infusion														Pre-dose	Relative to start of infusion																	
Hours		0	1	2	3	4	6	8	12	16	20	24	48	72	0	1	2	3	4	6	8	12	16	20	24	48								
GENERAL AND SAFETY ASSESSMENTS																																		
Informed consent	X																																	
Hospitalization																																		
Concomitant Medications																																		
Serious adverse events																																		
Adverse events																																		
Disease-related events																																		
Clinical Evaluation ^c	X	X										X	X	X	X																			
Vital signs, pulse oximetry ^d	X	X	X	X	X	X	X	X	X	X	X	X	X	X	X	X	X	X	X	X	X	X	X	X	X	X	X	X	X	X	X	X	X	X
ECG triplicate measurement ^e	X	X	X ^h									X			X ^h																			X
LABORATORY ASSESSMENTS																																		
Serum pregnancy test ^f	X	X																																
Coagulation	X	X					X					X	X	X	X														X	X	X	X	X	X
Hematology, Chemistry	X	X					X					X	X	X	X														X	X	X	X	X	X
Urinalysis	X	X																														X	X	
Hepatitis Serology	X																																	
INVESTIGATIONAL PRODUCT DOSING																																		
AMG 673 short term IV Infusion			X																															
PK ASSESSMENTS																																		
AMG 673 PK Collection		X	X			X						X	X		X	X					X	X					X	X	X	X	X	X	X	
DISEASE and BIOMARKER ASSESSMENTS																																		
Bone marrow assessments	X																															X	X	

Footnotes defined on next page of the table

Approved

EOS = End of Study; EOT = End of Treatment; SCR = Screening

^a The Dose Level Review Team may recommend to change timing of D5 within a window of ± 1 day. In this case, timing of the following visits would be adjusted accordingly.

^b In case of extended infusion-free interval, patients must be monitored per institutional practices.

^c Clinical evaluations will include physical exam, ECOG, and weight. Screening only: demographics, medical history, and height will also be obtained. Pre-dose clinical evaluation may occur up to 3 days prior to dose.

^d Vital signs / pulse oximetry will also be assessed prior to subject's discharge from hospital in order to detect possible signs and symptoms of infusion reactions.

^e ECGs are required per [section 7.3.8](#). ECG's: At screening 2 triplicates (total of 6 ECGs) should be done, at predose C1D1: 1 triplicate (total of 3 ECGs), post 1hr -end of infusion, 24 hours post dose and at EOS. Schedule for ECGs during cycle 1 also applies in case of intra-subject dose escalation, regardless of actual study cycle.

^f Serum pregnancy test will be performed for all females unless surgically sterile or > 2 years postmenopausal

^h Assessment should be taken at the end of infusion

Approved

Table 7. Schedule of Assessments: Doses D1-D5 (Cycle 2)

Cycle Day	Treatment Period																								EoT	EoS						
	1												5 ^b										6	7			8	14				
	Pre-dose	Relative to start of infusion											Pre-dose	Relative to start of infusion																		
	0	1	2	3	4	6	8	12	16	20	24	48	72	0	1	2	3	4	6	8	12	16	20	24	48							
GENERAL AND SAFETY ASSESSMENTS																																
Hospitalization																																
Concomitant Medications																																
Serious adverse events																																
Adverse events																																
Disease-related events																																
Clinical Evaluation ^c	X												X	X	X	X											X	X	X	X	X	X
Vital signs, pulse oximetry ^d	X		X	X	X	X	X	X	X	X	X	X	X	X		X	X	X	X	X	X	X	X	X	X	X	X	X	X	X	X	
ECG triplicate measurement ^e	X		X ^f									X				X ^f										X					X	
LABORATORY ASSESSMENTS																																
Coagulation	X						X					X	X	X	X												X	X	X	X	X	X
Hematology, Chemistry	X						X					X	X	X	X												X	X	X	X	X	X
Urinalysis	X													X																X	X	
Hepatitis Serology																																
INVESTIGATIONAL PRODUCT DOSING																																
AMG 673 short term IV infusion		X														X																
PK ASSESSMENTS																																
AMG 673 PK Collection	X		X				X					X	X		X					X	X					X	X	X	X	X	X	
DISEASE and BIOMARKER ASSESSMENTS																																
Bone marrow assessments																													X		X	

Approved

EOS = End of Study; EOT = End of Treatment; SCR = Screening

^a The Dose Level Review Team may recommend to change timing of D5 within a window of ±1 day. In this case, timing of the following visits would be adjusted accordingly.

^b In case of extended infusion-free interval, patients must be monitored per institutional practices.

^c Clinical evaluations will include physical exam, ECOG, and weight. Screening only: demographics, medical history, and height will also be obtained. Pre-dose clinical evaluation may occur up to 3 days prior to dose.

^d Vital signs / pulse oximetry will also be assessed prior to subject's discharge from hospital in order to detect possible signs and symptoms of infusion reactions.

^e ECGs are required per [section 7.3.8](#). ECG's: at predose C2D1: 1 triplicate (total of 3 ECGs), post 1hr -end of infusion, 24 hours post dose and at EOS.

^f Assessment should be taken at the end of infusion

Table 8. Schedule of Assessments: Doses D1-D5 (Cycle 3 and beyond)

Cycle Day	Treatment Period														14 ^b	EoT	EoS
	Pre-dose	1					Pre-dose	5 ^a									
		Relative to start of infusion						Relative to start of infusion									
Hours		0	1	2	3	4		0	1	2	3	4					
GENERAL AND SAFETY ASSESSMENTS																	
Informed consent																	
Hospitalization	at discretion of investigator																
Concomitant Medications	_____→																
Serious adverse events	_____→																
Adverse events	_____→																
Disease-related events	_____→																
Clinical Evaluation ^c	X						X								X	X	X
Vital signs, pulse oximetry ^d	X	X	X	X	X	X	X	X	X	X	X	X	X	X	X	X	X
ECG triplicate measurement ^e	X	X ^f						X ^f									X
LABORATORY ASSESSMENTS																	
Coagulation	X						X								X	X	X
Hematology, Chemistry	X						X								X	X	X
Urinalysis	X						X								X	X	
Hepatitis Serology																	
INVESTIGATIONAL PRODUCT DOSING																	
AMG 673 short term IV Infusion		X						X									
PK ASSESSMENTS																	
AMG 673 PK Collection	X	X			X	X							X				
DISEASE and BIOMARKER ASSESSMENTS																	
Bone marrow assessments															X		X

EOS = End of Study; EOT = End of Treatment; SCR = Screening

^a The Dose Level Review Team may recommend to change timing of D5 within a window of ±1 day. In this case, timing of the following visits would be adjusted accordingly.

^b In case of extended infusion-free interval, patients must be monitored per institutional practices.

^c Clinical evaluations will include physical exam, ECOG, and weight. Screening only: demographics, medical history, and height will also be obtained. Pre-dose clinical evaluation may occur up to 3 days prior to dose.

^d Vital signs / pulse oximetry will also be assessed prior to subject's discharge from hospital in order to detect possible signs and symptoms of infusion reactions.

^e ECGs are required per section 7.3.8. ECG's: at predose C3D1: 1 triplicate(total of 3 ECGs), post 1hr -end of infusion, 24 hours post dose and at EOS.

^f Assessment should be taken at the end of infusion

Approved

Table 9. Schedule of Assessments: Doses D1/D5/D12/D19 (Cycle 1)

Cycle Day	SCR	Treatment Period																																							EoT	EoS																					
	-14 to -1	1												5 ^a												12 ^a								13 ^a 14 ^a 15 ^a				19 ^a							20	21	22	28 ^b															
		Pre-dose						Relative to start of infusion						Pre-dose						Relative to start of infusion						Pre-dose		Relative to start of infusion				Pre-dose		Relative to start of infusion																													
Hours	0	1	2	3	4	6	8	12	16	20	24	48	72	dose	0	1	2	3	4	6	8	12	16	20	24	48		dose	0	1	4	6	8	12	16	20	24	48	72	dose	0	1	4	6	8	12	16	20	24	48	72												
GENERAL AND SAFETY ASSESSMENTS																																																															
Informed consent	X																																																														
Hospitalization		X																																																													
Concomitant Medications	X																																																														
Serious adverse events	X	X																																																													
Adverse events	X	X																																																													
Disease-related events																																																															
Clinical Evaluation ^c	X	X									X	X	X	X																																																	
Vital signs, pulse oximetry ^d	X	X	X	X	X	X	X	X	X	X	X	X	X	X	X	X	X	X	X	X	X	X	X	X	X	X	X	X	X	X	X	X	X	X	X	X	X	X	X	X	X	X	X	X	X	X	X	X	X	X	X	X	X	X	X								
ECG triplicate measurement ^e	X	X	X*								X				X*														X														X																				
LABORATORY ASSESSMENTS																																																															
Serum pregnancy test ^f	X	X																																																													
Coagulation	X	X				X				X	X	X	X									X	X	X	X					X			X	X	X	X	X	X	X	X							X	X	X	X	X	X	X	X	X	X	X	X					
Hematology, Chemistry	X	X				X				X	X	X	X									X	X	X	X					X			X	X	X	X	X	X	X	X							X	X	X	X	X	X	X	X	X	X	X	X	X	X			
Urinalysis	X	X																																																													
Hepatitis Serology	X																																																														
INVESTIGATIONAL PRODUCT DOSING																																																															
AMG 673 short term IV infusion		X																										X																																			
PK ASSESSMENTS																																																															
AMG 673 PK Collection		X	X			X				X	X	X	X	X	X	X	X	X	X	X	X	X	X	X	X	X*	X			X	X	X	X	X	X	X	X	X	X	X	X	X	X	X	X	X	X	X	X	X	X	X	X	X	X	X	X						
DISEASE and BIOMARKER ASSESSMENTS																																																															
Bone marrow assessments	X																																																												X	X	

EOS = End of Study; EOT = End of Treatment; SCR = Screening
 X* = at end of infusion perform corresponding assessment (ie, ECG at timepoint 1hr C3D1 with X* should be taken at end of infusion).
 NOTE: Use Table 6 in combination with Table 9 for Cycle 1, intra subject, dose step escalation, 4 dose schedule.
^a The Dose Level Review Team may recommend to change timing of D 5/12/19 within a window of ±1 day. In this case, timing of the following visits would be adjusted accordingly.
^b In case of extended infusion-free interval, patients must be monitored per institutional practices.
^c Clinical evaluations will include physical exam, ECOG, and weight. Screening only: demographics, medical history, and height will also be obtained. Pre-dose clinical evaluation may occur up to 3 days prior to dose.
^d Vital signs / pulse oximetry will also be assessed prior to subject's discharge from hospital in order to detect possible signs and symptoms of infusion reactions.
^e ECGs are required per section 7.3.8. ECG's: at predose, post 1hr -end of infusion, 24 hours post dose and at EOS.
^f Serum pregnancy test will be performed for all females unless surgically sterile or > 2 years postmenopausal

Approved

Table 10. Schedule of Assessments: Doses D1/D5/D12/D19 (Cycle 2)

Cycle Day	Treatment Period																												12 ^a	19 ^a	28 ^b	EoT	EoS																										
	1							5 ^b							6			7			8																																						
	Pre-dose	Relative to start of infusion														Pre-dose	Relative to start of infusion																	Pre-dose	Relative to start of infusion			Pre-dose			Relative to start of infusion																		
	0	1	2	3	4	6	8	12	16	20	24	48	72	0	1	2	3	4	6	8	12	16	20	24	48		0	1	4		0	1	4																										
GENERAL AND SAFETY ASSESSMENTS																																																											
Hospitalization	X																										at discretion of investigator																																
Concomitant Medications																										X																																	
Serious adverse events	X																									X																																	
Adverse events	X																									X																																	
Disease-related events																										X																																	
Clinical Evaluation ^c	X												X	X	X	X										X	X	X	X																														
Vital signs, pulse oximetry ^d	X	X	X	X	X	X	X	X	X	X	X	X	X	X	X	X	X	X	X	X	X	X	X	X	X	X	X	X	X	X																													
ECG triplicate measurement ^e	X	X*											X	X*												X	X	X*	X	X*				X	X	X																							
LABORATORY ASSESSMENTS																																																											
Coagulation	X												X	X	X	X									X	X	X	X																															
Hematology, Chemistry	X												X	X	X	X									X	X	X	X																															
Urinalysis	X												X													X				X				X	X	X																							
INVESTIGATIONAL PRODUCT DOSING																																																											
AMG 673 short term IV Infusion	X												X													X				X																													
PK ASSESSMENTS																																																											
AMG 673 PK Collection	X	X											X	X	X	X									X	X	X	X	X*	X	X*	X	X	X	X																								
DISEASE and BIOMARKER ASSESSMENTS																																																											
Bone marrow assessments																																																										X	X

EOS = End of Study; EOT = End of Treatment; SCR = Screening
 X* = at end of infusion perform corresponding assessment (ie, ECG at timepoint 1hr C3D1 with X* should be taken at end of infusion).
NOTE: Use Table 7 in combination with Table 10 for Cycle 2, 4 dose schedule.
^a The Dose Level Review Team may recommend to change timing of D5/12/19 within a window of ±1 day. In this case, timing of the following visits would be adjusted accordingly.
^b In case of extended infusion-free interval, patients must be monitored per institutional practices.
^c Clinical evaluations will include physical exam, ECOG, and weight. Screening only: demographics, medical history, and height will also be obtained. Pre-dose clinical evaluation may occur up to 3 days prior to dose.
^d Vital signs / pulse oximetry will also be assessed prior to subject’s discharge from hospital in order to detect possible signs and symptoms of infusion reactions.
^e ECGs are required per section 7.3.8. ECG's: at predose, post 1hr -end of infusion, 24 hours post dose and at EOS.

Approved

Table 11. Schedule of Assessments: Doses D1/D5/D12/D19 (Cycle 3 and Beyond)

Cycle Day	Treatment Period																28 ^b	EoT	EoS	
	1					5 ^a					12 ^a			19 ^a						
	Pre-dose	Relative to start of infusion				Pre-dose	Relative to start of infusion				Pre-dose	Relative to start of infusion		Pre-dose	Relative to start of infusion					
0		1	2	3	4		0	1	2	3		4	0		1	4	0	1	4	
GENERAL AND SAFETY ASSESSMENTS																				
Hospitalization		at discretion of investigator										at discretion of investigator								
Concomitant Medications		_____										X	_____							
Serious adverse events	X	_____										X	_____							
Adverse events	X	_____										X	_____							
Disease-related events		_____										X	_____							
Clinical Evaluation ^c	X					X					X				X			X	X	X
Vital signs, pulse oximetry ^d	X	X	X	X	X	X		X	X	X	X	X		X	X		X	X	X	X
ECG triplicate measurement ^e	X	X*					X*				X	X*	X	X*						X
LABORATORY ASSESSMENTS																				
Coagulation	X					X					X			X			X	X	X	
Hematology, Chemistry	X					X					X			X			X	X	X	
Urinalysis	X					X					X			X			X	X	X	
INVESTIGATIONAL PRODUCT DOSING																				
AMG 673 short term IV Infusion		X					X					X			X					
PK ASSESSMENTS																				
AMG 673 PK Collection	X	X			X	X					X	X	X*	X	X*	X	X	X	X	
DISEASE and BIOMARKER ASSESSMENTS																				
Bone marrow assessments																	X		X	

Footnotes defined on next page of the table

Approved

EOS = End of Study; EOT = End of Treatment; SCR = Screening

X* = at end of infusion perform corresponding assessment (ie, ECG at timepoint 1hr C3D1 with X* should be taken at end of infusion).

NOTE: Use [Table 8](#) in combination with [Table 11](#) for Cycle 3, 4 dose schedule.

^a The Dose Level Review Team may recommend to change timing of D 5/12/19 within a window of ± 1 day. In this case, timing of the following visits would be adjusted accordingly.

^b In case of extended infusion-free interval, patients must be monitored per institutional practices.

^c Clinical evaluations will include physical exam, ECOG, and weight. Screening only: demographics, medical history, and height will also be obtained. Pre-dose clinical evaluation may occur up to 3 days prior to dose.

^d Vital signs / pulse oximetry will also be assessed prior to subject's discharge from hospital in order to detect possible signs and symptoms of infusion reactions.

^e ECGs are required per [section 7.3.8](#). ECG's: at predose, post 1hr -end of infusion, 24 hours post dose and at EOS.

Approved

Table 12. Schedule of Assessments: Schedule B (Cycle 1)

Cycle Day	SCR -14 to -1	Treatment Period (14 Day Cycle)																			Only if no Cycle 2					EoT	EoS																
		1														2					15	16	17	18	19																		
		Hours relative to start of each QD infusion ^a																			Relative to Day 14 ^b																						
Hours	Pre-dose	0	1	2	3	4	6	8	12	16	20	Δ ^e 6			Δ ^e 6			Δ ^e 6	Δ ^e 6	1	6	12	24	48	72	96	120																
GENERAL AND SAFETY ASSESSMENTS																																											
Informed consent	X																																										
Hospitalization		_____→																																									
Concomitant Medications	X	_____→																																									
Serious adverse events	X	_____→																																									
Adverse events	X	X	_____→																																								
Disease-related events		_____→																																									
Clinical Evaluation ^c	X	X											X	X	X					X	X	X													X	X							
Vital signs, pulse oximetry ^d	X	X	X	X	X	X	X	X	X	X	X	X	X	X	X	X	X	X	X	X	X	X	X	X	X	X	X	X	X	X	X	X	X	X	X	X	X	X	X	X	X	X	
ECG triplicate measurement ^e	X	X	X ^e										X																												X		
LABORATORY ASSESSMENTS																																											
Serum pregnancy test ^f	X	X																																									
Coagulation	X	X						X						X	X	X					X																			X	X		
Hematology, Chemistry	X	X						X						X	X	X					X																			X	X		
Urinalysis	X	X												X						X																					X	X	
Hepatitis Serology	X																																										
INVESTIGATIONAL PRODUCT DOSING																																											
AMG 673 short term IV Infusion ^g			X											X	X	X	X	X	X	X	X	X	X	X	X	X	X	X	X	X	X	X	X	X	X	X	X	X	X	X	X	X	X
PK ASSESSMENTS																																											
AMG 673 PK Collection ⁱ		X		X			X	X						X	X	X	X	X	X	X	X									X	X	X	X	X	X	X	X	X	X	X	X	X	
DISEASE and BIOMARKER ASSESSMENTS																																											
Bone marrow assessments	X																																								X ^k		X

Footnotes defined on next page of the table

Approved

EOS = End of Study; EOT = End of Treatment; SCR = Screening

- ^a Assessments should be taken at the time specified (in hours) from the start of infusion on that day. If a time is not specified, all assessments and collections should be pre-dose.
- ^b The following assessments should be performed relative to the day 14 dose. Cycle 2 should begin immediately after Cycle 1 with no treatment free interval (see [Section 6.2.1.1.2](#)). The samples in dark gray are only collected if the subject will not initiate cycle 2 immediately after cycle 1. If cycle 2 is initiated immediately after cycle 1, then collect per [Table 14](#) (refer to footnote J).
- ^c Clinical evaluations will include physical exam, ECOG, and weight. Screening only: demographics, medical history, and height will also be obtained. Pre-dose clinical evaluation may occur up to 3 days prior to dose.
- ^d Vital signs / pulse oximetry must be collected as described above but may be collected at site more frequently per institutional policy or by recommendation of PI. Additional assessments do not need to be reported to EDC unless related to an adverse event but must be kept in source. Subjects will also be assessed prior to discharge from hospital in order to detect possible signs and symptoms of infusion reactions.
- ^e ECGs are required per [section 7.3.8](#). ECG's: At screening 2 triplicates (total of 6 ECGs) should be done, at predose C1D1: 1 triplicate (total of 3 ECGs), post 1hr -end of infusion, 24 hours post dose and at EOS. Schedule for ECGs during cycle 1 also applies in case of intra-subject dose escalation, regardless of actual study cycle.
- ^f Serum pregnancy test will be performed for all females unless surgically sterile or > 2 years postmenopausal
- ^g Refer to [Table 3](#) for planned dosing regimen

ⁱ This sample is optional. See Laboratory Manual for details on collection requirements.

^j Cycle 1, PK samples must always be collected on day 1. In addition, enhanced PK sampling, as described in [Table 13](#), is required at the time of step-up to the maximum planned dose. This is outlined [Table 3](#). If subject is not planned to immediately initiate cycle 2 (eg, due to DLTs), day 14-19 PK samples should be collected. If subject proceeds to Cycle 2, day 14 (post dose)-19 PK samples are not collected and sampling should occur as described in [Table 14](#).

^k During the same procedure, bone marrow samples will be collected for both response and biomarker assessments. This sample is to be collected after the last dose in Cycle 1 (ie, day 14).

Approved

Table 13. Schedule of Assessments: Schedule B (Cycle 1 Step-Up Dose Visit)

Step-Up Dose Day ^a	Treatment Period ^a											
	1											2
	Pre-dose	0	1	2	3	4	6	8	12	16	20	Pre
GENERAL AND SAFETY ASSESSMENTS												
Dexamethasone administration 1 hr before prior	X											
Clinical Evaluation ^c	X											X
Vital signs, pulse oximetry ^d	X	X	X	X	X	X	X	X	X	X	X	X
ECG triplicate measurement ^e	X	X ^f										X
LABORATORY ASSESSMENTS												
Coagulation	X						X					X
Hematology, Chemistry	X						X					X
Urinalysis	X											
INVESTIGATIONAL PRODUCT DOSING												
AMG 673 short term IV Infusion		X										X
PK ASSESSMENTS												
AMG 673 PK Collection ^f	X	X				X	X					X

EOS = End of Study; EOT = End of Treatment; SCR = Screening

^a Step-up doses are defined in Table 3. Day 1 in this schedule is each day where the planned dose is higher than the previous day.

^b Hours are calculated from the start of initial infusion of the higher dose (step-up)

^c Clinical evaluations will include physical exam, ECOG, and weight. Screening only: demographics, medical history, and height will also be obtained. Pre-dose clinical evaluation may occur up to 3 days prior to dose.

^d Vital signs / pulse oximetry must be collected as described above but may be collected at site more frequently per institutional policy or by recommendation of PI. Additional assessments do not need to be reported to EDC unless related to an adverse event, but must be kept in source.

^e ECGs are required per section 7.3.8. Triplicate ECGs are required at the times described above.

